- St. George's Respiratory Questionnaire (SGRQ) 22. It is divided into three subscales: symptoms (eight items), activity (16 items), and impacts (26 items). For each subscale and for the general questionnaire, the scores range from 0 (without deterioration) to 100 (maximum deterioration).

- COPD Assessment Test (CAT) 23. It consists of 8 questions with 5 possible answers valued from 0 to 5 (values close to 0: better health status)

-Pulmonary function: it will be measured with forced spirometry with a bronchodilatation test. According to a FEV1 / FVC ratio <70% and the FEV1 post bronchodilatation, patients will be classified in COPD: MILD FEV1> 80%; MODERATE: 50% - 80%; SEVERE: 30% -50%; VERY SEVERE: <30% 24.

-Dyspnea: Quantified by the modified scale of the Medical Research Council (mMRC) 25. It is part of the BODEx index (26).

-Pronostic: BODEx index (26). This index that can be scored from 1 to 3, depending on the variables: body mass index, FEV1, dyspnea (mMRC25 scale) and severe exacerbations of COPD.

-Anxiety and depression: they will be measured with the Goldberg's anxiety-depression scale (27).

-Hospital admissions in the last year (computerized medical history review).

Independent and confusing variables:

- Socio-demographic variables: age (date of birth), gender and level of studies.

-Date of diagnosis of COPD.

-Phenotype: non exacerbator; asthma- COPD; exacerbator with emphysema; exacerbator with chronic bronchitis (1).

Pharmacological treatment:

-Type of treatment: LABA, LAMA, LAMA + LABA, CI, SABA, SAMA, roflumilast.

-Pharmacological compliance: Assessed by the Morisky-Green test (28) that provides information about the causes of non-compliance. It consists of 4 questions with dichotomous response that must be introduced to the normal conversation with the patient.

Inhalation technique: practical test evaluating step by step the technique according to SEPAR and SEMFYC (29)

Comorbidities: hypertension, diabetes mellitus II, dyslipidaemia, depression and anxiety, joint disorders, cardiovascular disease, cardiovascular risk.

Tobacco: Not Smoker / Smoker / former smokers. Yes smoker or ex-smoker: no packages / year. If you smoke number of cigarettes / day. Nicotine dependence (Fargeström) (30), Motivation for change (Richmond) (31) and Phase of change (Prochaska and DiClemente) (32).

Alcohol: BU/week

Working exposure

Environmental exposure ambiental (contamination, tobacco...)

-Other variables:

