-Degree of participation in the intervention: 1 session/ 2 sessions/ 3 sessions/ ≥ 4 sessions

All the variables studied will be collected at baseline, prior to the intervention, and at 6, 12 and 24 months later, both in the intervention and in the control groups.

The control group will follow the usual treatment and follow-up and a visit will be scheduled to obtain the same variables as the intervention group, on a first visit, and at 6, 12 and 24 months.

Collection of data and sources of information:

Data analysis: Analysis will be carried out by intention to treat basis. All patients who signed their informed consent and who have completed the initial evaluation will be included in the analysis. The descriptive statistics of dependent, confusing and general variables will be calculated, both for the intervention group and for the control group and the homogeneity of the two groups for these variables will be checked at the beginning of the study. In all cases, a bilateral alpha error of 0.05 will be considered and the confidence intervals will be calculated at 95%. A variable will be calculated for each

measurement time (baseline, 6 months post-intervention and 12 and 24 months), which is the difference between the result of SGRQ and the other dependent variables of interest in each cut and the initial value, for each individual. Differences between groups and the confidence intervals of the difference to 95% will be calculated. An analysis of the variance of repeated measures (ANOVA) will be performed to evaluate the differences in time of dependent variables attributable to the effect of the intervention. It will adjust for the possible confusers, comorbidity, other interventions carried out, among others.

Difficulties and limitations of the study: This is a clinical trial in which health professionals who usually see the subject of study can know the group to which the patient belongs. They will "try to preserve masking in some important stages of the study: random allocation, evaluation of the main measures, statistical analysis of the data. On the other hand, the duration of the study can lead to long term loss to follow-up. To ensure the patient's adherence telephone location will be performed (at least three attempts per appointment, if the patient has not indicated that he does not want to participate) when missing the intervention sessions and a quarterly reminder telephone contact.

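### Every patient with a baseline is to be analysed by intention to treat, but no method for missed visits is stated, and a conventional repeated-measures ANOVA cannot include incomplete patients unless values are imputed

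*Combined protocol and SAP*

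**What the plan says.** All of this is in section 3, METHODOLOGY.

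- **Population.** "Analysis will be carried out by intention to treat basis", followed by "All patients who signed their informed consent and who have completed the initial evaluation will be included in the analysis".
- **Visits.** "All the variables studied will be collected at baseline, prior to the intervention, and at 6, 12 and 24 months later", in both arms.
- **Analysis.** Each patient's change from baseline is computed at each visit. Then "Differences between groups and the confidence intervals of the difference to 95% will be calculated", and "An analysis of the variance of repeated measures (ANOVA) will be performed to evaluate the differences in time of dependent variables". On covariates: "It will adjust for the possible confusers, comorbidity, other interventions carried out, among others".
- **Loss.** The limitations paragraph accepts that "the duration of the study can lead to long term loss to follow-up". It answers with telephone follow-up of missed sessions and a quarterly reminder call. The sample size paragraph allows 10%.
- **Masking.** The limitations paragraph says masking will be attempted for outcome evaluation and for the statistical analysis.

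The documents do not mention imputation, a mixed or likelihood-based model, a missing-data assumption or a sensitivity analysis.

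**The concern.** The inclusion rule and the named method pull apart as soon as a visit is missed. The rule says who is analysed; nothing says what happens to the values they do not have. A conventional repeated-measures ANOVA needs a complete row per patient. The per-visit comparison of changes leaves out anyone without that visit, and a patient with a baseline only has no change score at all.

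Without a written rule, the handling of absent values is left to be settled once the data exist. The default in most software is to analyse complete patients only. That gives a fair comparison only if those patients represent their arms, or if selection distorts both arms alike. In a 24-month trial of a behavioural programme against usual care, reasons for leaving may differ by arm.

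**Working it through.** **1. The plan's sample size.** Inputs from the sample size paragraph: difference 3.51, SD 11.33, two-sided alpha 0.05, power 80%, loss 10%.

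n = 2 × (1.96 + 0.8416)² × 11.33² / 3.51² = 163.6 per arm; 163.6 / 0.9 = 181.7, so 182.

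This reproduces the stated 182. The 10% enters once, as a single overall allowance, and leaves 182 × 0.9 = 163.8 patients per arm. Power by the same formula, Φ(3.51 / (11.33 × √(2/n)) − 1.96), is 84.0% at n = 182, 80.1% at 164 and 79.9% at 163.

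**2. What each named analysis can use.**

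| Patient | Inclusion rule | Per-visit change | Conventional ANOVA |
|---|---|---|---|
| All four visits | in | in at each visit | in |
| One follow-up visit missed | in | out at that visit | out |
| Baseline only | in | out throughout | out |

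A software check agrees: a standard repeated-measures ANOVA routine ran on 20 subjects at four times, and stopped with an unbalanced-data error when one visit of one subject was deleted.

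**3. Power at the plan's 10%.** Assumptions: 11.33 is the SD of change; visits are equally correlated at r = 0.5, 0.7 or 0.8; a 10% cumulative dropout is spread evenly over the three follow-up visits. Power comes from the information matrix of a mixed model with a common baseline mean, three visit means and three arm-by-visit terms.

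| r | All available data | Complete cases |
|---|---|---|
| 0.5 | 90.2% | 89.9% |
| 0.7 | 86.5% | 86.0% |
| 0.8 | 84.6% | 84.0% |

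The gain is under 1 point. The ANOVA's own group-by-time test, with an assumed constant effect of 3.51 at each follow-up (noncentral F, degrees of freedom 3 and 3(2n − 2)), has 87.2% power at 182 per arm and 83.2% at 164.

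**4. Bias.** The dropout patterns here are assumptions; the documents give none. The true effect is 3.51 at every follow-up. Dropout occurs before month 12 and before month 24, with a log-odds that rises by b per SD of worsening in the last observed change. In a selective arm b = 1 (odds × 2.7); otherwise b = 0. A hazard of about 5% per interval gives 1 − 0.95² = 9.75% cumulative loss.

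| Loss depends on outcome in | Complete-case 24-month difference (true 3.51) |
|---|---|
| Intervention arm only | about 3.9 to 4.1 |
| Control arm only | about 2.95 to 3.0 |
| Both arms, same dependence on raw change | about 3.4 |

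In the first row, 4.0 to 4.1 applies when loss in the intervention arm is set to about 10%. About 3.9 applies when that arm keeps the intercept calibrated without an effect, so that it loses 7.4%. In the third row loss is 9.7% in control and 7.4% in intervention, because improved patients leave less often.

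With no true effect, selective loss in the intervention arm alone gives a spurious difference of about 0.5. In 3,000 simulated trials per setting the complete-case ANOVA then rejected in 8.0 to 8.5%, against 4.6 to 5.2% for the mixed model (covariance taken as known). With the same dependence in both arms and no true effect there is no bias, and the ANOVA rejected in 4.4 to 5.0%.

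**The case against.** The strongest reply is that the plan is silent rather than contradictory. It does not say that incomplete patients are dropped. An ANOVA after imputation would include everyone, and some authors use the term loosely for a mixed model. That stands: a reader might infer that the plan excludes incomplete patients, and the text does not support that. Silence is still the defect, because the method as named does not deliver the inclusion rule.

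Second, the plan has mitigations: retention calls, a 10% allowance, and attempted masking of the analysis, which makes a late choice harder to steer. These lessen the concern. None says how a value that is still absent is analysed, and the allowance protects power, not against selective loss.

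Third, a reader might infer that the trial is underpowered. It is not shown to be. Differences of 7 to 9 points between all data and complete cases appear only if 10% are missed independently at each visit (for example 86.8% against 78.1% at r = 0.7). The plan's arithmetic uses the 10% once, so there is no reason to read it that way or to ask whether it is per visit. Having no margin beyond the allowance is normal for such a calculation.

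Fourth, the selective-dropout patterns are invented for illustration, and bias can run either way. That is correct, and limits the claim to possible bias.

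**Conclusion.** The point holds as a gap that should be fixed. Everyone with a baseline is to be analysed, and the plan does not say how patients with missed visits get into the analysis; the conventional form of the named ANOVA leaves them out unless values are imputed.

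The size is conditional. With about 10% loss that depends on outcome in one arm only, the error is roughly 0.4 to 0.6 SGRQ units on a true 3.51, upwards or downwards. With the same dependence on raw change in both arms it is zero under no effect, and about 0.1 towards zero under the planned effect. These figures rest on the assumed dropout models, on equal correlation and on 11.33 being the SD of change. It would go too far to conclude that the trial's result will be biased, or that equal dependence in both arms always makes a complete-case analysis safe. The benefit of the change is protection against bias under a weaker assumption (missing at random) and agreement with the plan's own inclusion rule; at the planned loss it is not a gain in power.

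**What to change.** In the data analysis paragraph of section 3:

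1. For SGRQ and the other continuous outcomes (for example CAT and FEV1), replace the repeated-measures ANOVA with a likelihood-based linear mixed model on all available visits. Put baseline in the outcome vector with one mean common to both arms; include visit, arm-by-visit at follow-up, an unstructured covariance and the plan's baseline adjustment variables. Report the arm difference and 95% CI at each visit from this model. Multiple imputation under missing at random is an acceptable alternative if prespecified.
2. Apply a corresponding all-available-data model to the ordinal visit measures (mMRC and BODEx).
3. State how data after death are treated.
4. Add one missing-not-at-random sensitivity analysis for SGRQ.

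Admissions, listed as "Hospital admissions in the last year (computerized medical history review"), come from records rather than from attendance and can stay outside this change.

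The cost is wording and slightly more analysis work; no extra patients, visits or measurements. The main analysis will rely on missing at random, which item 4 probes. Patients with only a baseline will be included but will add little to the comparison between arms.

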#### Ethical considerations and Confidentiality of the data

This study will follow strictly the current regulations and national regulations related to the ethics committees and data protection rules.

All recruited patients will be informed verbally and in writing of the objectives, methodology, tests and interventions they will receive if they participate in the study, and asked to sign informed consent. This document will be written in a language understood by the patient. The information will be treated anonymously. No user identification data will be computerized, and the whole study will be developed in accordance with the rules of good research practices. The study will be submitted to the CEIC of the IDIAP Jordi Gol.

The processing, communication and assignment of personal data will be in accordance with the provisions of Organic Law 15/1999, of December 13, on the protection of personal data. According to what is established by law, the participant may exercise their right of access, modification, opposition and cancellation of data.

#### Additional procedures derived from the study

Group intervention: 4 to 6 visits will be scheduled with the reference nurse, 20 "in duration and separated 15 days.

Contents: Knowledge of the disease. Healthy lifestyle habits. Correct technique for the use of inhalers. Symptom control skills. Strategies for confronting the disease.

Specific contents: Behavioral change techniques, knowledge about COPD, adherence to the therapeutic plan (pharmacological and non-pharmacological), abandonment of the tobacco habit, alcoholic beverages, avoidance of environmental and working exposures, recommended vaccinations, inhalation techniques, knowledge about drugs used, basic respiratory exercises, energy saving techniques, relaxation techniques, recognition and performance of exacerbations, physical exercise enhancement, correct nutrition, sexuality.

The visits will be customized according to the clinical profile of the patient, the phenotype, the specific needs, their preferences and the stage of the change process in which he is found to be. All the sessions will be monitored by means of a specific track record where all activities / interventions will be collected, and the data collected (stage of the process of change, life habits: tobacco, diet, exercise, respiratory physiotherapy, inhalers ...). It will advise and facilitate attendance at the sessions of possible caregivers.

The behavioral components common to all the sessions will be: the setting of objectives, the motivational interview, providing feedback and behavioral cognitive therapy.

All learning will be based on educational material that will be provided to the patient: audiovisual, written educational material, links to web pages with useful and proven information (for example papsf ("Primary Health Care"), "the virtual nurse" or "caregiver" ) and, above all, the tutored practice of skills.

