## **3. METHODOLOGY**

Design: Multicentre randomized clinical trial

Reference population: Patients with a diagnosis of moderate-severe COPD treated with inhaled bronchodilators.

Study population: Patients with a diagnosis of moderate and / or severe COPD , with bronchodilator treatment in PC Centers, that meet the criteria for inclusion in the study.

Inclusion criteria: Patients who have been visited at least once last year at the center with diagnosis of COPD (J44), with a moderate airflow limitation (FEV1 between 50% - 80%) or severe airflow limitation(FEV1 between 30 % - 50%), treated with bronchodilators, and who accept to participate in the study.

Exclusion criteria

- Patients only receiving home attention (Z74)
- Patients with mental disorders and / or severe mental disorders that do not allow following the sessions
- Patients diagnosed with asthma, tuberculosis or other chronic respiratory diseases
- Patients receiving chronic home oxygen therapy (OCD).
- Patients with terminal disease.

Sample size and sample procedure: Accepting an alpha risk of 0.05 and a beta risk lower than 0.2 in a bilateral contrast, 182 subjects in the first group and 182 in the second are need to detect a difference equal to or greater than 3.51 Units in the St George's Respiratory Questionnaire. It is assumed that the common standard deviation is 11.33. A follow-up loss of 10% has been estimated. Patients will be contacted by phone, via sms, internet or at office consultation (according to the authorization given to the e-CAP) by offering participation in the study and a visit will be scheduled to explain the study and to obtain the signed informed consent and the collection of data.

The random distribution to the groups will be carried out centrally, through a computer program that generates the random numbers managed by a remote investigator to recruiters. The allocation of each patient will be hidden in an envelope that will be opened when the professional has confirmed that he complies with the selection criteria and the patient has signed the informed consent.

Variables

-Quality related to Health (QVRS) will be measured with specific and standardized self-administered questionnaires, validated by our environment:

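### If outcomes cluster by reference nurse in the intervention arm, or the treatment effect varies by nurse, the planned analysis gives intervals that are too narrow and power below the stated 80%

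*Combined protocol and SAP*

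**What the plan says.** **Delivery.** The section on additional procedures derived from the study states that "4 to 6 visits will be scheduled with the reference nurse". The content is behavioural (motivational interviewing, cognitive behavioural work, feedback, supervised practice of skills) and is tailored to the individual patient. Controls follow usual care. Section 3 does not say who provides that care, or whether the same nurses see patients in both arms.

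**Sample size (section 3).** The calculation is set up as "Accepting an alpha risk of 0.05 and a beta risk lower than 0.2 in a bilateral contrast". The stated aim is to "detect a difference equal to or greater than 3.51 Units in the St George's Respiratory Questionnaire", with 10% loss to follow-up allowed for. On variability, the plan says: "It is assumed that the common standard deviation is 11.33". The resulting size is "182 subjects in the first group and 182 in the second". No ICC or design effect appears.

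**Analysis (section 3).** Between-group differences in change from baseline are given with 95% intervals. In addition, "An analysis of the variance of repeated measures (ANOVA) will be performed to evaluate the differences in time of dependent variables". The list of adjustment variables is left open-ended. Neither nurse nor centre is named in it, and the list of variables to be collected has no identifier for either.

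**Allocation (section 3).** Individual patients are allocated centrally "through a computer program that generates the random numbers". Stratification by centre is neither stated nor excluded.

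**The concern.** In a tailored behavioural programme, the nurse's skill is part of the treatment. Intervention patients of one nurse share that influence, so their outcomes may be correlated in a way that controls' outcomes are not. Section 4 intends the results to support recommendations on how nurses should carry out the intervention and to be spread to other nursing staff. Inference of that kind reaches beyond the participating nurses, so variation between nurses belongs in the standard error.

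If it is left out, the standard error of the treatment effect is understated. The nominal 5% test then rejects too often under the null, and the nominal 95% intervals cover too rarely. The planned power has almost no margin to absorb this, as the first step of the working shows.

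**Working it through.** **1. The plan's own figure.** Inputs from section 3: difference 3.51, SD 11.33, two-sided alpha 0.05, power 80%, loss 10%.

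- n per arm = 2 × (1.96 + 0.8416)² × 11.33² / 3.51² = 163.6, so 164 evaluable. 164 / 0.9 = 182.2, or 183 rounded up, against the stated 182.
- With 182 × 0.9 = 163.8 evaluable per arm, SE = 11.33 × √(2 / 163.8) = 1.252, and 3.51 / 1.252 = 2.804. Power = Φ(2.804 − 1.96) = 80.1%.

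The stated size therefore reproduces, under independence.

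**2. Clustering in the intervention arm only.** The ICC and the number m of evaluable intervention patients per nurse are assumptions, because the documents give neither. Total SD stays at 11.33.

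- Design effect in the intervention arm: DE = 1 + (m − 1) × ICC.
- Ratio of true to naive SE: r = √((DE + 1) / 2).
- Type I error of the naive test: 2 × (1 − Φ(1.96 / r)).
- Power of a test that uses the correct SE: Φ(2.804 / r − 1.96).

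| ICC | m | DE | r | Type I error, naive test | Power, correct SE |
|---|---|---|---|---|---|
| 0 | any | 1.00 | 1.000 | 5.0% | 80.1% |
| 0.01 | 2 | 1.01 | 1.002 | 5.1% | 79.9% |
| 0.02 | 5 | 1.08 | 1.020 | 5.5% | 78.5% |
| 0.05 | 10 | 1.45 | 1.107 | 7.7% | 71.7% |

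For the last row: DE = 1 + 9 × 0.05 = 1.45; r = √(2.45 / 2) = 1.107; 1.96 / 1.107 = 1.771, which gives 7.7%; and Φ(2.804 / 1.107 − 1.96) = Φ(0.573) = 71.7%. A correct interval would be 11% wider than the naive one.

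The last two columns belong to different analyses. The naive test keeps some apparent power by rejecting too often: in the last row it is Φ((2.804 − 1.96) / 1.107), about 78%, which is still below 80%. The formulas use normal quantiles. With about 163.8 / 10 ≈ 16 nurses, the correct analysis would lose slightly more through its degrees of freedom.

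**3. Effects shared by both arms.** These were checked by simulation with 328 completers, individual randomisation and an ordinary two-group comparison that ignores the cluster.

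| Scenario | Type I error | Power |
|---|---|---|
| Centre effect shared by both arms, 18 centres, ICC 0.05, simple randomisation | 5.5% | 80.2% |
| Same, allocation balanced by centre | 4.7% | 80.5% |
| Nurse effect shared by both arms, ICC 0.05, 10 to 40 patients per nurse | 4.7–4.9% | 80.0–80.3% |
| Provider variance of 5% acting on intervention patients only, 18 providers, simple randomisation | 7.9% | 77.1% (naive test) |

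A shared effect does no material harm. Variation specific to the intervention does.

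**The case against.** **Centre.** A reader might infer that ignoring centre also makes the intervals too narrow, since the trial is multicentre. The documents do not support that. Patients are randomised individually, so a centre main effect falls on both arms and largely cancels, as the simulation confirms. Only a treatment effect that varies across centres would matter.

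**Shared nurses.** The nurses are patients' reference nurses, not trial-only therapists. The limitations paragraph of section 3 says that the professionals who usually see the patients may know the allocation. This is compatible with the same nurses serving both arms, though it does not settle the matter. If they do, the nurse main effect cancels in the same way and only nurse-by-treatment variation counts, so the loss is smaller than in the intervention-arm-only calculation. This objection stands, and it is why the point is conditional.

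**Size.** A reader might also infer that the 80% is certainly and seriously overstated. With few patients per nurse and a small ICC the loss is negligible. More extreme inputs, such as ICC 0.05 with 20 patients per nurse, bring power to 64%. They imply only about 8 nurses for the whole intervention arm (163.8 / 20), and nothing in the documents supports that.

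**Open-ended adjustment.** The adjustment wording would permit a centre term. It does not prespecify one, and it would not supply a nurse effect specific to the intervention.

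What remains is the direction: any positive nurse variance specific to the intervention, with more than one patient per nurse, makes the naive interval too narrow.

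**Conclusion.** The point holds conditionally. The sample size arithmetic is right on its own inputs, but its 80% power, like the planned intervals, rests on an independence assumption that nurse delivery puts in doubt. Over the assumed range, the consequence runs from negligible (5.1% type I error, 79.9% power) to material (7.7%, 72%). These figures assume clustering in the intervention arm only, equal caseloads, total SD 11.33 and 10% loss. The documents supply neither ICC nor caseload and do not say whether nurses see both arms, so no single figure can be defended. The claim is limited to nurse variation that acts on the intervention arm or on the treatment effect. It does not extend to effects common to both arms.

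**What to change.** 1. Record centre and delivering nurse for each patient and, for controls, their usual reference nurse. State the number of centres and nurses, the expected caseload, and whether nurses see both arms.
2. Replace the repeated-measures ANOVA with a linear mixed model for the repeated measurements that has a centre effect and a random nurse effect in the intervention arm (a partially nested model). If nurses see both arms, use a random nurse-by-treatment effect instead. Use Satterthwaite or Kenward-Roger degrees of freedom.
3. Restate the 80% power as holding under independence, and give a range over assumed ICC and caseload. Do not enrol more patients on this account. Holding 80% would take 190 recruited per arm at ICC 0.02 with 5 per nurse, or 224 at 0.05 with 10, but both figures rest on inputs that the documents do not provide.

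The cost is one data field, a change of model wording, somewhat wider intervals and a less favourable power statement. The nurse field should be captured prospectively, because the model cannot be fitted reliably without it. If nurse variance proves close to zero, the mixed model costs little.

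Stratifying the random list by centre is a separate option that improves balance. It does not deal with nurse clustering.
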